## **3. Research Design and Methods**

### **Prospective Validation of a Multimodal Imaging Large Model**

#### **(I) Study Design Type and Methodology**

This study is a single-center prospective observational study, aiming to conduct prospective validation and optimization of the established medical multimodal large model based on real-time collected clinical multimodal data (imaging, medical records, laboratory tests, reports, etc.). No additional interventions will be imposed on patients' diagnosis and treatment processes during the study; relevant data will only be collected synchronously during routine clinical examinations and diagnostic procedures, making it a non-interventional, minimal-risk prospective study.

During the study period, all newly diagnosed cases meeting the inclusion criteria will be consecutively enrolled. The research team will conduct prospective inference and performance validation of the multimodal medical large model based on imaging findings, EMR text, and laboratory test data, systematically evaluating the model's performance in tasks such as disease diagnosis, lesion localization, and report generation. Study results will be compared with clinicians' actual diagnostic conclusions and pathological gold standards to verify the model's generalization ability and clinical applicability in real-world scenarios.

The overall study protocol includes the following phases:

1. **Case recruitment and data collection:** Patients undergoing imaging examinations in the hospital will be consecutively recruited according to pre-defined inclusion criteria. Study data are derived from routine clinical workflows, covering imaging data, EMRs, laboratory results, and radiology reports. All data will undergo de-identification and quality control before being entered into the study database, with only the minimum necessary information retained.

2. **Model application and inference:** The research team will deploy the multimodal model in the hospital's secure computing environment. For each enrolled patient, the model will automatically generate disease predictions, lesion localization results, and diagnostic reports based on their imaging data and corresponding clinical text.

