3. **Clinical comparison and result documentation:** The model outputs will be subject to double-blind evaluation by radiologists and clinicians from relevant departments, compared with the final pathological or clinically confirmed results, and the accuracy, consistency, and interpretability of model predictions will be documented.

4. **Model iteration and continuous validation:** On the premise of ensuring ethical and privacy compliance, the research team will use newly collected data for continuous model fine-tuning and validation, analyzing its stability and robustness across different disease types, devices, and operational conditions.

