## **(III) Patient Inclusion, Exclusion, and Withdrawal Criteria**

### **Inclusion Criteria**

1. Adult patients aged  $\geq 18$  years;
2. Undergoing imaging examinations (CT, MRI, ultrasound, etc.) in the hospital during the study period;
3. Examination items corresponding to the disease types or systems focused on by the study (hepatobiliary and pancreatic system);
4. Possessing at least complete imaging data and radiology diagnostic reports, with relevant medical record information as supplementary modalities;
5. Patients or their legal representatives signing an informed consent form, agreeing to the use of their de-identified data for scientific research model validation;
6. Case data passing quality review, with good imaging quality and standardized text records.

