### **Exclusion Criteria**

1. Patients refusing to sign the informed consent form;
2. Imaging data unassessable due to severe motion artifacts, incomplete scanning, or equipment malfunctions;
3. Severe lack of clinical data or inability to match with imaging data;
4. Special pathological cases or post-operative cases (e.g., extensive resection, significant structural changes after radiotherapy) that affect the consistency of model analysis;
5. Data samples with privacy protection or legal risks.

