### **Withdrawal Criteria**

1. Discovery of non-compliance with inclusion criteria or fulfillment of exclusion criteria after enrollment;

2. Failure of data de-identification or file corruption;
3. Patients or their legal representatives withdrawing consent during the study period;
4. Occurrence of data security incidents or ethical risks, leading to exclusion as determined by the IRB after review.

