#### **(IV) Detailed Research Protocol**

##### **Research Data Sources**

Data for this study are derived from patients undergoing routine clinical examinations in the hospital during the study period. Data collection is accomplished relying on the hospital's existing information systems, without imposing additional burdens on patients or interfering with diagnosis and treatment processes. All data are real-world multimodal information generated in routine clinical practice, mainly including:

- Medical imaging data from the Department of Radiology, covering original images and reconstructed sequences such as CT, MRI, and ultrasound, as well as manual annotations, masks, or structured descriptions, which serve as reference standards for model validation;
- Radiology diagnostic reports, including examination findings, diagnostic conclusions, and physician recommendations. All images undergo unified format conversion (e.g., DICOM to NIfTI) and quality assessment before being imported into the study database, with sequences containing artifacts or defects excluded;
- Text data from the electronic medical record system, including admission records, discharge summaries, progress notes, and surgical records. Prior to import, text data undergo automated de-identification to remove sensitive information such as names, hospital admission numbers, ID card numbers, and contact information, retaining only key clinical course points relevant to the research objectives;
- Structured laboratory data from the laboratory information system, including quantitative data such as complete blood count, biochemical indicators, tumor markers, and coagulation function, which are aligned with imaging examinations via timestamps to support cross-modal feature fusion and quantitative analysis of disease states in the model.

All research data undergo rigorous de-identification before being imported into the analysis environment, with only the minimum necessary information required for the study retained. Data collection and usage comply with the Personal Information Protection Law, Data Security Law, and the hospital's ethical requirements. All patients sign a written informed consent form prior to enrollment, explicitly agreeing to the use of their de-identified data for scientific research model validation and performance optimization. The entire research process is conducted under the approval and supervision of the IRB.

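### Three unequal image-quality rules let readable but imperfect imaging be removed before inference, while the protocol claims real-world performance

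*Protocol*

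**What the plan says.** Image quality is governed at three points of Section 3 of the protocol:

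- **Inclusion Criteria, item 6** (case level): "Case data passing quality review, with good imaging quality and standardized text records". No scale, threshold or assessor is given for good quality.
- **Exclusion Criteria, item 2**: "Imaging data unassessable due to severe motion artifacts, incomplete scanning, or equipment malfunctions". This reaches only imaging that cannot be assessed.
- **Research Data Sources** (sequence level): images undergo "quality assessment before being imported into the study database", "with sequences containing artifacts or defects excluded". There is no severity limit and no reference to assessability.

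The Withdrawal Criteria add a later route out: "Discovery of non-compliance with inclusion criteria or fulfillment of exclusion criteria after enrollment". The Statistical Analysis Procedures nevertheless describe an intention-to-treat analysis of every enrolled case.

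The claims are broad. The design section intends to "verify the model's generalization ability and clinical applicability in real-world scenarios", and phase 4 of the same section speaks of "analyzing its stability and robustness across different disease types, devices, and operational conditions". Research Data Sources states: "All data are real-world multimodal information generated in routine clinical practice". The sample size text also promises an accurate evaluation under real-world clinical conditions.

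**The concern.** A validation study estimates performance for the set of scans that it lets through. If readable scans with minor faults are removed before the model sees them, the estimate applies to cleaner input than the hospital produces. A model would be expected to do worse on degraded images, so its accuracy would probably look better than in routine use. Image degradation is also one of the ways in which operating conditions differ, so some of the variation that phase 4 wants to study may be lost.

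A second risk concerns the comparison with clinicians. Their diagnoses come from routine care and presumably rest on every sequence acquired. If only the model's input is filtered, the two are not judged on the same material.

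Because the rules are unequal and one is undefined, two people applying the protocol could also assemble different study sets from the same patients.

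**Working it through.** The protocol states no figure on this point, so there is none to reproduce. The check is a comparison of the rules, followed by an illustration of what would determine the size.

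**Step 1. The same imaging under each rule.**

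| Imaging | Inclusion item 6 | Exclusion item 2 | Import rule |
|---|---|---|---|
| Clean | passes | not excluded | imported |
| Mild or moderate artifact, still readable | depends on an undefined standard | not excluded | affected sequence removed |
| Unassessable because of a severe fault | fails | excluded | removed |

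The rules agree on the first and last rows. They part on the middle row, where the severity and assessability limits of exclusion item 2 lose their effect once any artifact triggers removal at import.

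**Step 2. What happens to the patient.** The import rule acts on sequences. A patient who loses one might (a) drop out, for instance by no longer meeting inclusion item 4 on completeness of imaging, or (b) stay in with fewer sequences. The protocol does not say which.

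**Step 3. If the case is lost (a).** Let q be the share of readable degraded cases and d the drop in model accuracy on them. Then:

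accuracy in all cases = (1 − q) × clean accuracy + q × (clean accuracy − d) = clean accuracy − q × d,

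so model accuracy is overstated by q × d. The protocol gives neither q nor d. Purely as an illustration, take the 85% planning value as the clean accuracy, with assumed shares of 5–30% and drops of 10–30 points:

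| q (assumed) | d (assumed) | q × d | Accuracy in all cases |
|---|---|---|---|
| 5% | 10 points | 0.5 points | 84.5% |
| 10% | 20 points | 2.0 points | 83.0% |
| 20% | 20 points | 4.0 points | 81.0% |
| 30% | 30 points | 9.0 points | 76.0% |

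Milder assumptions (shares of 10–30%, drops of 5–15 points) give 0.10 × 5 = 0.5 to 0.30 × 15 = 4.5 points. For scale, the 95% half-width for one accuracy of 85% in 2000 patients is 1.96 × √(0.85 × 0.15 / 2000) = 0.0156, about 1.6 points.

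**Step 4. The difference from manual diagnosis.** The 5-point planning difference (85% against 80%) is model minus manual. If whole cases are lost, manual results on them are lost too, and the bias in the difference is q × (d for the model − d for manual diagnosis). With q = 20% and a model drop of 20 points, assumed manual drops of 10, 20 and 30 points give 0.20 × 10 = +2 points, 0, and 0.20 × (−10) = −2 points. The sign is open.

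**Step 5. If the case stays in (b).** The formula in step 3 does not apply. The model works on fewer but cleaner sequences, and clinicians presumably had all of them. The comparison is uneven, with no computable direction.

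**Step 6. Timing and blinding.** The import rule acts before inference. Inclusion item 6 can also act later, through withdrawal. The double-blind evaluation in phase 3 concerns model outputs; nothing says that image quality is judged without knowledge of those outputs.

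**The case against.** Several points on the other side stand.

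- A reader might infer that the inclusion and exclusion criteria contradict each other. They do not: a case must meet every inclusion criterion and no exclusion criterion, so a stricter inclusion item beside a looser exclusion item is redundant. The exclusion item could even be read as the working floor for good quality.
- The import rule stands in a data-preparation sentence beside format conversion, and defects may include file or conversion faults. It need not remove patients.
- A reader might set 0.5–4.5 points against the 5-point planning difference. That compares unlike quantities: the first is a bias in model accuracy alone and rests on assumed inputs, whereas the second is a difference between model and manual diagnosis.
- A reader might conclude that robustness can no longer be tested. The secondary outcome on generalization concerns devices, disease types and populations, none of which is image quality, and operational conditions are left undefined. Filtering may thin these comparisons but does not remove them.
- Nothing here argues against standardized text records or against discarding corrupt files.

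These points limit the size and reach of the concern. They do not reconcile the import rule with the exclusion criterion, settle the fate of a patient who loses a sequence, or make a filtered set represent routine imaging.

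**Conclusion.** The point holds as an unreconciled selection rule. Followed as written, the protocol can remove readable but imperfect imaging before inference while claiming real-world performance and robustness. Overstatement of the model's accuracy for routine use is the probable direction. It is an inference that assumes the model does worse on degraded scans, not something that the document shows.

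The size cannot be computed from the protocol. The 0.5 to 9 points illustrated above depend wholly on assumed shares and drops, and apply only if whole cases are lost. The effect on the model-minus-manual difference is unknown in size and sign. The inconsistency itself needs no figure. It should be settled before enrollment, because an analysis plan cannot recover sequences that were never imported.

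**What to change.** Apply one rule in all three places, namely the unassessable criterion already in exclusion item 2:

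- In Research Data Sources, limit removal to sequences that are unassessable or technically corrupt.
- Align the imaging-quality wording of inclusion item 6 with that rule, and leave its requirement on text records as it is.
- State whether the rule acts on the case or the sequence, and what happens to a patient who loses a sequence.
- Judge quality before inference, by someone blind to model output.
- Keep assessable imperfect scans in the primary analysis.
- Report the number of exclusions with reasons and, where the quality review already records a grade, results by quality.

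If the sponsor prefers the stricter filter, the three places should still be reconciled, and the real-world and robustness claims should be limited to quality-filtered scans.

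The cost is protocol wording, a blinded quality judgement and some extra analysis. The scans already exist from routine care. Reported accuracy may be slightly lower.

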### **Exclusion Criteria**

1. Patients refusing to sign the informed consent form;
2. Imaging data unassessable due to severe motion artifacts, incomplete scanning, or equipment malfunctions;
3. Severe lack of clinical data or inability to match with imaging data;
4. Special pathological cases or post-operative cases (e.g., extensive resection, significant structural changes after radiotherapy) that affect the consistency of model analysis;
5. Data samples with privacy protection or legal risks.

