#### **Statistical Analysis Procedures**

This study adopts intention-to-treat (ITT) analysis as the primary analytical strategy, conducting systematic statistical analysis on data from all enrolled cases. First, descriptive statistics are performed to summarize the baseline characteristics of patients, including age, gender, disease type, and imaging equipment source. Continuous variables are presented as mean  $\pm$  standard deviation or median depending on their distribution type, while categorical variables are expressed as frequencies. Inter-group differences are analyzed using appropriate statistical methods based on data characteristics: the t-test is used for normally distributed data, and the Mann–Whitney U test is used for non-normally distributed data.

In the analysis of primary outcome indicators, this study focuses on evaluating the model's performance in three core tasks: disease diagnosis, lesion localization, and report generation. For the disease diagnosis task, clinical final diagnosis or pathological results are used as the gold standard to calculate AUC, Sensitivity, Specificity, Accuracy, and F1-score, and receiver operating characteristic (ROC) curves are plotted to comprehensively assess the model's classification ability. For the lesion localization and segmentation task, expert annotations are used as references to calculate the Dice coefficient and Hausdorff distance, measuring the model's performance in lesion recognition range and boundary precision. For the report generation task, model-generated reports are compared with radiologists' reports at the text level, and natural language generation metrics such as BLEU, ROUGE, and CIDEr are used to evaluate language quality and semantic consistency.

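### Exclusion 4 is undefined and tied to the model, and can be applied after enrolment without masking; this is in tension with analysing all enrolled cases and can inflate reported performance

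*Protocol*

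**What the plan says.** All of the relevant text is in section 3 of the protocol.

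- **Exclusion Criteria, item 4:** "Special pathological cases or post-operative cases (e.g., extensive resection, significant structural changes after radiotherapy) that affect the consistency of model analysis". The bracketed examples are all post-treatment changes. What makes a case pathologically special is not stated.
- **Withdrawal Criteria, item 1:** "Discovery of non-compliance with inclusion criteria or fulfillment of exclusion criteria after enrollment". No time limit is set, and nobody is required to be masked.
- **Inclusion Criteria, item 6:** "Case data passing quality review, with good imaging quality and standardized text records". Withdrawal item 1 reopens this criterion as well.
- **Study Design Type and Methodology:** "all newly diagnosed cases meeting the inclusion criteria will be consecutively enrolled", and "For each enrolled patient, the model will automatically generate disease predictions, lesion localization results, and diagnostic reports". The results are meant to show generalization and applicability in real-world use.
- **Statistical Analysis Procedures:** "This study adopts intention-to-treat (ITT) analysis as the primary analytical strategy, conducting systematic statistical analysis on data from all enrolled cases". For the diagnosis task, "clinical final diagnosis or pathological results are used as the gold standard".

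**The concern.** In a validation study, the set of cases on which the model is scored should not depend on how the model copes with them. Exclusion 4 makes that link in its wording, and withdrawal criterion 1 allows it to be used after the model has run. The person who decides that a case is special may by then know both the final diagnosis and the model's output. If the cases removed this way are harder than average, accuracy and related measures in the remainder look better than they would in the consecutive series that the protocol says it enrols.

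The primary analysis set is also unclear. One section analyses every enrolled case. Another lets enrolled cases be withdrawn, and no text says whether they stay in the analysis. The ITT label does not settle this: the study is observational and imposes no intervention, so there is no assignment to respect.

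**Working it through.** **Step 1: sequence of events.**

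1. Patients are enrolled consecutively (section 3 (I), phase 1).
2. The model runs on each enrolled patient (phase 2).
3. Outputs are compared with pathology or the confirmed clinical diagnosis (phase 3).
4. Withdrawal criterion 1 can act at any time after enrolment, so also after steps 2 and 3.

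The double-blind evaluation in phase 3 covers the rating of model outputs. It does not cover eligibility decisions. Nothing in the protocol therefore prevents a case from being declared special when output and truth are both known.

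**Step 2: what can be settled beforehand.** Prior extensive resection and post-radiotherapy change are matters of history or anatomy, and section 3 (IV) lists surgical records among the data sources. That part of exclusion 4 can be judged before inference. The special pathological part cannot be judged objectively at any time, because it has no definition.

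**Step 3: effect on reported accuracy.** The protocol states no figure on this point to reproduce: it mentions data disqualification but gives no rate. From the Sample Size Estimation Process come a model accuracy of 85%, a manual accuracy of 80% and about 2000 patients. The share removed (f) and the model's accuracy in removed cases (q) are my assumptions.

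With A the accuracy in all enrolled cases, reported accuracy after removal = (A − f·q) / (1 − f).

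For A = 85%:

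| | q = 85% | q = 80% | q = 70% | q = 50% |
|---|---|---|---|---|
| f = 5% | 85.0% | 85.3% | 85.8% | 86.8% |
| f = 10% | 85.0% | 85.6% | 86.7% | 88.9% |

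- Smallest gain among harder cases: (0.85 − 0.05×0.80)/0.95 = 0.810/0.95 = 85.3%, or +0.3 points.
- Largest gain: (0.85 − 0.10×0.50)/0.90 = 0.800/0.90 = 88.9%, or +3.9 points.
- If removed cases are easier (f = 10%, q = 90%): 0.760/0.90 = 84.4%, a small loss.
- If removal followed model error directly, dropping 100 misclassified cases of 2000 would turn 1700/2000 = 85.0% into 1700/1900 = 89.5%.

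**Step 4: effect on the model-versus-manual difference.** With B the manual accuracy in all enrolled cases (80%) and r the manual accuracy in removed cases, the reported difference is [(A − B) − f·(q − r)] / (1 − f). Take f = 10% and q = 50%:

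- r = 45%, the same 5-point lead as overall: (0.05 − 0.10×0.05)/0.90 = 5.0 points, unchanged.
- r = 80%, manual reading unaffected by these cases: (0.05 + 0.10×0.30)/0.90 = 8.9 points.

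The difference grows only if the removed cases are relatively worse for the model than for manual reading. That is plausible, since exclusion 4 refers to the model alone, but the documents do not show it.

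**The case against.** The clause about model consistency can be read as a rationale (altered anatomy) and not as an instruction to inspect the model's output. Withdrawal criterion 1 lists a ground for withdrawal and does not say that the case leaves the analysis, so it could be read together with the all-enrolled rule. Image-quality control is placed before entry into the study database, which comes ahead of inference. Handling of late-found ineligible cases is often left to a statistical analysis plan, and that plan is not shown.

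Much of this stands. A reader might infer that the protocol tells staff to remove cases after seeing model errors, or that the two sections flatly contradict each other. Neither is stated: the text permits late, unmasked removal and is silent on whether withdrawn cases are still analysed. A reader might also infer that every performance measure is biased upward. The documents do not support that. The share and difficulty of removed cases are unknown, a higher Hausdorff distance is worse, and no effect is shown for the text metrics, which are scored against radiologists' reports.

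What the objection does not remove is the undefined category, the lack of any rule on when and by whom it is judged, and the mislabelled primary analysis set. Eligibility and withdrawal rules belong to the protocol, so a later analysis plan would inherit these gaps.

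**Conclusion.** The point holds as a defect in how the rules are written. Exclusion 4 is open-ended and tied to the model, withdrawal criterion 1 lets it operate after enrolment without masking, and both are in tension with analysing all enrolled cases and with a consecutive, real-world validation. The rules can inflate model performance; that they will do so is not shown.

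The size cannot be derived from the documents. Under the assumed 5–10% removed and 80–50% model accuracy in those cases, an all-enrolled accuracy of 85% would be reported about 0.3 to 3.9 points too high, and unchanged if the removed cases are no harder. It is tempting to set such a gain against the planned 5-point effect and conclude that removal could create most of it. That mixes two quantities: the gain is in model accuracy, whereas the planned effect is model minus manual, which shifts in the model's favour only if removal favours the model over manual reading.

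**What to change.** 1. **Exclusion 4:** delete the special pathological category and the closing clause about the model, or replace them with objective conditions documented before the index examination, such as prior extensive resection or radiotherapy.
2. **Timing and masking:** require eligibility and quality decisions to be made before inference, or by someone masked to model output and pathology.
3. **Removal from the analysis:** limit it to withdrawn consent, failed de-identification, file corruption or an IRB decision. Keep cases found ineligible later in the primary set, and report results with and without them.
4. **Analysis set:** replace ITT with all enrolled patients, defined as in item 3, and align the Withdrawal Criteria with the Statistical Analysis Procedures.
5. **Reporting:** give the number and reason for every exclusion.

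The cost is protocol wording, best settled before the scheduled start on November 15, 2026. The downside is that reported accuracy may be slightly lower and more variable.
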